In Durban, participants will be recruited from the **Addington Hospital Sinathando HIV Clinic, Clairwood Hospital HIV Clinic, Wentworth Clinic, and King Dinizulu Hospital**. The four clinics together manage an active caseload of over 10,000 HIV patients. The study will be managed centrally from the University of KwaZulu-Natal (UKZN), which operates numerous HIV clinical research projects and employs research staff with experience in recruitment, enrollment, participant monitoring, informed consent, data collection, phlebotomy, and laboratory processing, storage, and testing.

C. Eligibility Criteria

We will recruit persons with HIV-infection who are in care at any of the five above clinics who meet the following inclusion criteria:

1. Inclusion criteria:

- a. In care at a public HIV clinic within a PEPFAR-focus sub-Saharan African country (South Africa or Uganda) and living within 100 kilometers of the clinic
- b. Age \geq 18 years at the time of enrollment
- c. Currently prescribed first-line (non-nucleoside reverse transcriptase inhibitor [NNRTI]-based) ART for at least 5 months. Switches within first line regimens, including NNRTI and nucleos(t)ide backbone changes are allowed.
- d. Detectable plasma viral load $>$ 1,000 copies/mL and/or dried blood spot viral load $>$ 1,000 copies/mL within 90 days of enrollment

2. Exclusion criteria:

- a. Known prior drug resistance
- b. Prior exposure to PI-based ART
- c. Current clinical indication to start PI-based ART
- d. Not planning to remain in the clinic catchment area for the next nine months

3. Eligibility criteria rationale

The study aims to enroll HIV-infected adults on first-line ART with a newly identified instance of a viral load $>$ 1,000 copies/mL. Patients attending study clinics implementing dried blood spots (DBS) for

virologic testing will be eligible, provided they have a DBS viral load >1,000 copies/mL [25, 26], or if they undergo repeat plasma viral load testing to confirm a viral load >1,000 copies/mL. We aim to exclude those with known prior resistance, those on second line therapy, and those at high risk for default from study because of immigration out of the clinic catchment area.

D. Recruitment and Enrollment

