Pregnant women in care at HIV clinics that also offer antenatal HIV services will be eligible for enrollment in this study. Their inclusion will be critical to ensure that study results are generalizable to this population, who stand to gain as much if not more from studies intended to elucidate optimal strategies of HIV care. To ensure safeguarding of pregnant women and their fetuses, procedures will be slightly altered for this population. First, to confirm pregnancy status, women under 50 years of age will undergo urine β -human chorionic gonadotropin (HCG) testing at the enrollment visit. Those who test positive will be referred to antenatal care in addition to the remainder of study procedures. Additionally, pregnant women in the standard of care arm will have a slightly altered visit schedule, such that they will return in 1 month after study enrollment for a repeat viral load test (as opposed to 2-3 months). This recommendation is in keeping with South African Prevention of Mother-to-Child Transmission Guidelines [27], and is intended to maximize chances of viral re-suppression prior to delivery.

Figure 2. Study Schema

G. Randomization

Consenting participants will be randomized by the [REDCap randomization module](#) to the standard of care (SOC) or the resistance-testing based (RT) arm (Figure 2). In brief, after screening has been completed, eligibility confirmed, and informed consent forms signed, a study participant is given a unique consecutive identification number in REDCap. The randomization field is selected, and the research assistant is informed which arm the participant has been selected for by the application. Randomization will be in blocks of 4 and stratified by study site, pregnancy, and duration of time since ART initiation (less than versus greater than one year). Randomization will be stratified by ART duration because of the potential heterogeneity in resistance rates between those with early treatment failure from primary drug resistance versus late failure due to acquired drug resistance. Strategy allocation will be unblinded to participants or clinic staff.

V. STUDY PROCEDURES FOR PARTICIPANTS RANDOMIZED TO STANDARD OF CARE ARM

A. Visit 1-SOC: Baseline Visit for Standard of Care Participants

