We made the following provisions to account for the COVID-19 epidemic period. Study enrollment is complete and no new participants will be enrolled. Additionally, all study-specific visits have been cancelled in both Uganda and South Africa during this period, until such time that local regulations and authorities recommend for the resumption of non-essential activities. In the interim we will take the following steps in each country :

1. In Uganda, REVAMP study staff will work with HIV clinic staff who are already in the clinic to collect these specimens during the participants' regularly scheduled HIV clinic visits if they occur during the Visit 3 follow-up window. If participants do present to clinic for routine services, study staff will call them to administer study questionnaires via phone call where participant phone contact information is available, rather than in-person study visits.
2. In South Africa, we have discussed study procedures with both clinic leadership and the local IRB. Both recommended continuing of procedures under the following conditions:
 - a. Participants will be seen when attending for routine clinical care and or coming in for treatment collection and will not be asked to attend for study purposes.
 - b. The study is reviewing participants that are potentially failing treatment and require a viral load test. The study will provide both viral load testing and resistance testing to those who have a detectable viral load per study protocol, which will advise further management of the participants.
 - c. On presentation at the clinic patients will undergo routine screening for COVID 19 by clinic staff. Participants who screen positive will not be seen by research staff. Those that screen negative will have blood drawn by study nurses.
 - d. Study funding will provide private transport to and from clinics for all study staff. No public transport will be used
 - e. Study nurses are expected not to spend more than 10 to 15 minutes with participants during the study visit and will remain 2 metres away for all procedures aside from blood collection
 - f. All study nurses have been trained on proper use of personal protective equipment and supplied with masks, gloves, face shields, and hand sanitizer which they will strictly adhere to for all participant encounters

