All research assistants will complete training through the CITI biomedical human subjects research course or a refresher course, as indicated. Only research staff fluent in the local languages (Runyankole or IsiZulu) will conduct informed consent and survey procedures. Study staff certified in phlebotomy will complete any blood collection procedures. Study staff will maintain active research ethics certification and attend any annual research ethics conferences as mandated by local policy at their institutions.

2. Clinical Study Staff

Prior to study initiation, clinical study staff will complete a training in the interpretation of HIV-1 resistance testing results and management of virologic failure. The course will be designed and directed by study Co-Investigators Drs. [name], [name], and/or [name] and conducted at the study sites. The course will include a review of major non-nucleoside and nucleos(t)ide reverse transcriptase inhibitor mutations, second-line regimen options, drug-drug interactions, common drug toxicities, and a case-based learning session.

B. Data Monitoring

After review of the study protocol with National Institutes of Health officials, the proposed study is considered to present minimal risk to participants given that subjects will complete questionnaires and undergo routine HIV monitoring with viral load and resistance testing per standard guidelines, and no investigational agents or tests will be used. Therefore, we will not establish a formal Data and Safety Monitoring Board. The study statistician and co-investigators will meet annually to perform the following activities: a) review the research protocol and plans for data and safety monitoring; b) review progress of the trial, including analysis of data quality and timeliness; subject recruitment, randomization and retention; subject risk versus benefit; and other factors that may affect outcome. c) review serious and unexpected adverse event reports, provide commentary, and provide oversight to ensure that reports are relayed to individual IRBs; d) review proposed modifications to the study prior to their implementation. Meetings will be held every twelve months beginning in Year 2 of the study. We will also have an independent data monitor who will annually review blinded summaries of outcome and adverse event data and provide a report to study investigators on recommendations amending the study.

C. Adverse and Unexpected Event Reporting

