To assess our sample size calculation, we first estimated predicted rates of viral suppression in the SOC arm (Figure 3). To do so, we combined estimated suppression rates for those who remain on first line therapy and those who are switched to second line therapy, due to a persistent elevation in viral load >1,000 copies/mL. Multiple studies have reported that approximately 40% of people (range 27% - 59%) with an initial detectable viral load on first-line therapy load will re-suppress while remaining on first line therapy in the interim [2, 8-10]. Among those who do remain on first-line therapy, we estimate that only approximately 50% will remain suppressed on first-line therapy, owing to both high rates of underlying resistance [8], and sub-optimal adherence. Among patients in the SOC arm with persistent virologic failure on repeat testing who are switched to second line therapy, we expect approximately 80% will re-suppress [35]. In summary, we predict that net re-suppression rates in the standard of care arm compiling those who remain on first-line therapy (20%) and those who switch to second line therapy (48%), will be approximately 68%. While comparative rates of re-suppression with resistance testing are unknown, we hypothesize that resistance testing has the potential to significantly improve viral suppression rates, particularly because rates of resistance at first-line failure are common in the region (65-90%) [7, 8, 36], and because those who are switched to a protease inhibitor-based combination regimen are highly likely to re-suppress [37-39].

Figure 3. Schema of estimated outcomes for participants in the standard of care arm.

Assuming a 68% viral suppression rate in the SOC arm, using a two-sample test of binomial proportions with a Type I error rate of 5%, and allowing for a 5% rate of invalid tests, we compute a 69%, 88%, and 97% power to detect a difference in suppression rates of 8, 10, and 12%, respectively (Table 3). Based on these estimates, we plan to enroll approximately 840 total participants into the study to allow sufficient power to detect a programmatically meaningful 10% superiority rate of viral suppression in the RT arm.

Table 3. Sample Size Estimates

Viral Suppression Rate in SOC Arm	Viral Suppression Rate in RT Arm	Difference in Outcome Rate	α	Sample Size (per group)	Invalid Test Rate	Power
68%	76%	8%	0.05	420	5%	0.69
68%	78%	10%	0.05	420	5%	0.88
68%	80%	12%	0.05	420	5%	0.97

B. Efficacy Analyses

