Study data coordinators will perform routine reviews of data quality to identify unusual values and missing data entries. Initial analyses will include common exploratory data analyses, table construction, and scatterplots to assist in data quality control, randomization balance, and exploring for possible outliers or leverage points. For our analysis of the primary outcome, we will use a two-sample test of binomial proportions to compare the proportions of participants in each arm who achieve virologic suppression at the study conclusion. For our primary analysis we will conduct an intention to treat analysis. For this analysis, any study participant without a confirmed viral load result at the 9-month study endpoint will be considered as having a detectable viral load (failure). In secondary analyses, we will conduct as-treated analyses for any study participants who do not complete resistance testing in the RT arm or participant who do receive resistance testing in the SOC arm, as documented by clinic records. We will also conduct a sensitivity analysis by censoring participants who are lost-to-follow-up during study procedures and do not have a recorded viral load at study conclusion. The unadjusted comparison of outcome rates will be followed by adjusted comparisons via logistic regression, adjusting for other confounding factors that may explain any heterogeneity or possibly confound assigned treatment and outcome, despite treatment randomization.

The primary analyses will be followed by similar statistical analyses of secondary endpoints including the proportions suppressed on first-line therapy, rates of resistance, rates of retention in care, and the 9-month mortality rate. We will compare health related quality of life measures within participants between baseline and study conclusion using paired t-tests.

C. Economic Analyses

1. Budget Impact Analysis

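### The primary test ignores the factors used to stratify randomization; a pre-specified stratified analysis would gain a little precision at almost no cost

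*Combined protocol and SAP*

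**What the plan says.** Section IV.G (Randomization): "Randomization will be in blocks of 4 and stratified by study site, pregnancy, and duration of time since ART initiation", the last split at one year. The reason given for the ART-duration factor is that resistance rates may differ between early and late failure.

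Section X.B.4 (Efficacy Analysis Plan), primary outcome: "we will use a two-sample test of binomial proportions to compare the proportions of participants in each arm who achieve virologic suppression". A participant with no confirmed 9-month result counts as a failure. Then: "The unadjusted comparison of outcome rates will be followed by adjusted comparisons via logistic regression, adjusting for other confounding factors". Those covariates are not listed.

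Section X.A (Sample Size) powers the trial on the same kind of test, "using a two-sample test of binomial proportions with a Type I error rate of 5%, and allowing for a 5% rate of invalid tests".

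Study site is not defined for randomization. Section IV.B names two clinics in Mbarara and four in Durban. Section IV.C recruits patients "in care at any of the five above clinics". Section V.C speaks of site principal investigators in Mbarara and in Durban. That allows 6, 5 or 2 sites.

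**The concern.** Stratified blocks balance the arms within strata, so differences between strata add little to the error of the treatment comparison. An unstratified test still counts those differences as noise. When the strata are prognostic, its standard error is too large, its real type I error falls below 5%, and some precision already paid for in the design is lost. The plan itself gives a reason to expect a prognostic effect: Section IV.G points to differing resistance by ART duration, and Section X.A links underlying resistance to poor suppression on first-line therapy.

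A second issue concerns only the follow-up model. With no covariates named, the choice stays open in an open-label trial. The stratification factors are the natural ones to fix in advance.

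**Working it through.** **1. The plan's own power.** Inputs from Section X.A: 420 per arm less 5% invalid tests, 420 × 0.95 = 399; 68% in the standard arm; differences of 8, 10 and 12 points; α = 0.05, taken as two-sided because the plan does not say. Without continuity correction, power is 0.712, 0.891 and 0.973; with it, 0.684, 0.875 and 0.967. The printed 0.69, 0.88 and 0.97 fit the corrected test better. A one-sided test (0.81, 0.94, 0.99) does not fit. All figures below are uncorrected unless stated.

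**2. Formulas.** With d the risk difference, held constant across strata:
- Unstratified power = Φ((d − 1.96·SE_pooled)/SE_true)
- Stratified power = Φ((d − 1.96·SE_within)/SE_true)
- Type I error of the unstratified test = 2(1 − Φ(1.96·√(marginal variance/within-stratum variance)))

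**3. One case in full.** 399 per arm, 68% v 78%, two equal strata 20 points apart (assumed): 58% and 78% in the standard arm, 68% and 88% in the testing arm.
- SE_pooled = √(2 × 0.73 × 0.27/399) = 0.03143
- SE_within = √(2 × ½(0.63 × 0.37 + 0.83 × 0.17)/399) = √(2 × 0.1871/399) = 0.03062
- SE_true = √((0.2076 + 0.1616)/399) = 0.03042
- Unstratified: Φ((0.10 − 0.06160)/0.03042) = Φ(1.262) = 0.897
- Stratified: Φ((0.10 − 0.06002)/0.03042) = Φ(1.314) = 0.906
- Type I error, unstratified: marginal variance 0.68 × 0.32 = 0.2176, within-stratum 0.2076; 2(1 − Φ(1.96 × 1.0238)) = 0.045

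**4. Range of gaps, two equal strata.** Basis A removes invalid tests, as in Section X.A (399 per arm, 68% v 78%). Basis B follows Section X.B.4 and counts missing as failure, assuming 5% missing: 420 per arm, 0.68 × 0.95 = 64.6% v 0.78 × 0.95 = 74.1%. Gaps are before missingness.

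| Gap (points) | A: power, unstratified v stratified | A: type I error, unstratified | B: power, unstratified v stratified | B: type I error, unstratified | B: 95% CI half-width, unstratified v stratified |
|---|---|---|---|---|---|
| 0 | 0.891 v 0.891 | 0.050 | 0.849 v 0.849 | 0.050 | 6.20 v 6.20 |
| 10 | 0.892 v 0.894 | 0.049 | 0.850 v 0.853 | 0.049 | 6.20 v 6.17 |
| 20 | 0.897 v 0.906 | 0.045 | 0.854 v 0.864 | 0.046 | 6.20 v 6.07 |
| 30 | 0.904 v 0.924 | 0.038 | 0.861 v 0.882 | 0.040 | 6.20 v 5.90 |

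Unequal strata gain less. With a 20-point gap, a stratum holding 15% of participants gives 0.894 v 0.898 (A) and 0.852 v 0.857 (B); one holding 5% gives 0.892 v 0.893 (A) and 0.850 v 0.852 (B).

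**5. Number of strata.** Sites × 2 pregnancy levels × 2 ART-duration levels gives 2 × 4 = 8, 5 × 4 = 20 or 6 × 4 = 24. These are maxima, since Section IV.F ties the enrollment of pregnant women to clinics that offer antenatal HIV services.

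**6. Cost of many small strata.** Simulation on basis B: 200,000 runs per case, blocks of 4, and, as assumptions, equal-sized sites, 5% pregnant and 15% under one year on ART. Power:

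| Strata | No gap: unstratified v CMH | 20-point ART-duration gap: unstratified v CMH |
|---|---|---|
| 8 | 0.850 v 0.849 | 0.851 v 0.856 |
| 20 | 0.850 v 0.848 | 0.853 v 0.857 |
| 24 | 0.851 v 0.849 | 0.852 v 0.855 |

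With the gap, type I error is 0.047 to 0.048 unstratified and 0.049 to 0.050 for CMH. Coverage of the Mantel-Haenszel 95% CI is 94.9% to 95.0%.

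**7. Strata with nobody in one arm.** In the same simulation at least one occurs in 37%, 94% and 97% of runs for 8, 20 and 24 strata, holding on average 0.6, 2.6 and 3.3 participants. Merging only pregnancy levels removes them all when sites are equal. With assumed shares of 40, 10, 35, 8, 5 and 2% over six sites, a one-arm stratum remains in about 30% of runs.

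**8. Continuity correction.** With no gap, adding one lowers power from 0.891 to 0.875 (A) and from 0.849 to 0.831 (B), more than stratification gains for gaps up to 20 points.

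**The case against.** The strongest case for leaving the plan alone is that nothing is broken. The primary test is pre-specified, valid and the one the trial was powered on. The gain is small and rests on gaps and stratum shares that the documents do not give. Where only ART duration matters, the simulated gain for a 20-point gap is 0.3 to 0.5 points, and where no factor matters there is a loss of 0.1 to 0.2. A carelessly specified replacement could lose more than it gains through a continuity correction.

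Timing also matters. Section VII says "Study enrollment is complete and no new participants will be enrolled", allocation is open, and Visit 3 results go straight to clinic staff. Section IX.B plans an "independent data monitor who will annually review blinded summaries of outcome and adverse event data", but that does not show that nobody has compared outcomes by arm. A late change of primary test in an open-label trial would carry a credibility cost.

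These points stand as conditions on the fix. They do not remove the mismatch between design and analysis, and the follow-up logistic model does not either: it comes after the primary comparison and commits to none of the three factors.

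A reader might go further and infer that the planned test is invalid, that it inflates type I error, or that the logistic model leaves the strata out. The documents do not support this. The calculated type I error is at or below 5%, and the covariate list is open, so the factors are neither included nor excluded.

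**Conclusion.** The point holds as a small, low-cost improvement, not as an error. The primary analysis does not use the randomization strata, and no analysis names them. Stratifying would add about 0 to 1 power point for gaps up to 20 points and about 2 points only for two equal strata 30 points apart; it would cost at most about 0.2 points if the strata are not prognostic. This rests on assumed gaps and shares, a constant risk difference across strata, a two-sided 5% test and no continuity correction.

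A reader might infer that the trial is underpowered for want of stratification. The figures do not show that. The drop from 0.891 to 0.849 between the two bases comes from counting an assumed 5% missing as failures, and the gain from stratifying is nearly the same on both.

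**What to change.** In a dated SAP version, finalised before outcomes by arm are examined:

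- Make one named method primary: the Mantel-Haenszel stratified risk difference with 95% CI, tested by CMH without continuity correction, over the randomization strata. Keep missing as failure.
- Define study site at the level used in the REDCap randomization.
- State a pooling rule that uses allocation counts only and continues until every stratum has both arms: for example, pregnancy levels first, then ART-duration levels within site, then sites within country.
- Keep the unadjusted two-sample test as supportive.
- Name the three factors in the follow-up logistic model.

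If outcomes by arm have already been seen, keep the planned test as primary and report the stratified analysis as supportive. The site definition and the named covariates are still worth adding, dated as such.

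The cost is SAP wording. The three factors are fixed at randomization, so no extra participants, visits or data are needed.

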The goal of this study is to determine whether addition of routine resistance testing, to guide management of virologic failure and sustain the successful completion of the HIV continuum of care, improves clinical outcomes and reduces costs for patients with virologic failure on first-line therapy in sub-Saharan Africa. We will enroll patients in care at public HIV clinics in Uganda and South Africa who have virologic failure on a first-line ART regimen, into a randomized controlled trial to complete the following aims:

- 1) Aim 1: Estimate the effectiveness of resistance test-based management of virologic failure (resistance testing arm), versus viral-load based management per WHO guidelines (standard of care arm).** We hypothesize that resistance testing-based management will be superior to standard of care management as measured by the proportion of patients with undetectable viral load 9 months after detection of virologic failure.
- 2) Aim 2: Evaluate the cost effectiveness of resistance-test versus viral load-based management of virologic failure in sub-Saharan Africa.** We hypothesize that resistance testing will be cost effective, because the cost of the assay will be offset by downstream cost savings through reduced use of second line therapy.

We intend that results of this study will be a useful resource for public health programmers, ministries of health and multinational partners to optimize the clinical management of virologic failure in the region.

[figure not shown]
III. BACKGROUND AND SIGNIFICANCE

In an effort to optimize the global HIV care continuum and foster sustained control of the HIV epidemic, the Joint United Nations Programme on HIV/AIDS (UNAIDS) has set a “90-90-90” treatment target for 2020 [2]. Achievement of this goal would mean, in part, that 90% of those receiving antiretroviral therapy (ART) sustain an undetectable HIV RNA viral load (viral load). At the epicenter of the epidemic in sub-Saharan Africa, however, rates of virologic suppression remain well below that goal; indeed, a systematic review of virologic suppression in the sub-Saharan African region found that only 2 in 3 patients maintain virologic suppression over two years of observation [3]. To maintain the goal of achieving 90% sustained virologic suppression, management of virologic failure must be optimized.

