The study design is an open-label, randomized controlled trial. The study will be conducted at study sites in Uganda and South Africa. The study population will include HIV-infected patients on first-line antiretroviral therapy with a recent viral load >1,000 copies/milliliter (mL). Eligible participants will be randomized to the WHO-based standard of care for management of virologic failure or immediate resistance testing with use of results to guide ART regimen decisions. The study will add the use of a diagnostic test, HIV-1 RNA resistance testing to clinical management of participants in the resistance testing arm, but all other clinical care including provision of ART therapy will be done by clinic sites in keeping with local HIV guidelines. The primary outcome of interest will be viral suppression (<200 copies/mL) at 9 months after study enrollment, and will be assessed using an intention to treat analysis, where missing or absent results will be considered failures. Secondary outcomes of interest will be viral suppression below the limit of assay detection, viral suppression on continuation of first-line (non-nucleoside reverse transcriptase inhibitor [NNRTI]-based) therapy, drug resistance at study conclusion, and mortality, among others. We will analyze primary data collected during the trial to conduct an economic analysis with the goal of estimating the cost-effectiveness of resistance testing versus standard of care.

B. Study Sites

1. Uganda

The Immune Suppression Syndrome (ISS) clinic at the Mbarara Regional Referral Hospital (MRRH) and its partner clinic across the street, the **Mbarara Municipal Clinic**, are PEPFAR-supported clinics, which, in combination, follow more than 20,000 patients with HIV/AIDS and have an established clinical research infrastructure. The clinics employ over 50 clinical care staff including nurses, clinicians, pharmacists, counselors, phlebotomists, patient trackers, and administrative staff. The clinics serve as the primary research sites for the MGH-MUST Global Health Collaborative, which employs an additional 60 research staff with expertise in recruitment, enrollment, participant monitoring, informed consent, data collection, phlebotomy, and laboratory storage and testing.

2. South Africa

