1. Primary Outcome of Interest

Proportion of patients with a laboratory confirmed suppressed viral load, as defined by <200 copies/mL, at study conclusion (Visit 3).

2. Rationale for Primary Outcome of Interest

We have chosen this as our primary outcome to ensure a balanced outcome assessment 9 months after study initiation, standardization of viral load results across sites with different viral load testing platforms, and because it is an accepted international standard for other international studies of virologic suppression [39, 40].

3. Secondary Outcomes of Interest

- a. Proportion of patients with an undetectable viral load (below limit of detection) at study conclusion
- b. Proportion of patients with an undetectable viral load on first-line (NNRTI-based) therapy at study conclusion
- c. Proportion of patients with International AIDS Society-defined drug resistance mutations to their current regimen ^[41]. As part of this analysis, we will also evaluate for minority drug resistance.
- d. Total patient care costs, including diagnostic testing and ART costs for the study duration
- e. Retention in HIV clinical care at study completion
- f. 9-month mortality rate
- g. Change in health-related quality of life from baseline to 9 months

4. Efficacy Analysis Plan

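### The primary-endpoint rules conflict after the COVID-19 amendment and between arms: a late closure-visit viral load can be scored either way, and the nine months start at different points.

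*Combined protocol and SAP*

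**What the plan says.** **What is scored, and when.** Section X.B.1 defines the primary outcome "at study conclusion (Visit 3"). The primary comparison in X.B.4 is of those who "achieve virologic suppression at the study conclusion". Section IV.A instead gives "viral suppression (<200 copies/mL) at 9 months after study enrollment", and fails participants whose result is lacking. The failure rule in X.B.4 is tied to month 9: "any study participant without a confirmed viral load result at the 9-month study endpoint will be considered as having a detectable viral load (failure").

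**Where the nine months start.**
- Aim 1: "9 months after detection of virologic failure". Under IV.C.1 the entry viral load may be "1,000 copies/mL within 90 days of enrollment", so detection can precede enrollment by up to 90 days.
- IV.A, and V.C for SOC: enrollment.
- VI.B for RT: the visit is booked at the end of Visit 2-RT for about nine months later. The next sentence says this is meant to match the SOC duration.
- X.B.2: the aim is a "balanced outcome assessment 9 months after study initiation".

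**COVID-19 text.** Sections V.E and VI.D postpone home tracking. Sections VI.C and VII accept that some visits will miss the Visit 3 timeline and provide a closure visit once the pandemic eases, with no latest date. Both also refer to a Visit 3 follow-up window, but the visible text gives no limits for it.

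**Sensitivity analysis.** The one planned analysis for missing outcomes is "censoring participants who are lost-to-follow-up during study procedures and do not have a recorded viral load at study conclusion".

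**The concern.** Before COVID-19, study conclusion, Visit 3 and month 9 were roughly the same time. The amendment separated them, and Section X was not updated: it mentions neither COVID-19 nor closure visits. A suppressed closure-visit result is a success under X.B.1 and, read literally, a failure under the X.B.4 rule. The planned sensitivity analysis does not help, because a late attender does have a recorded viral load.

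The difference in time origin is separate and does not depend on COVID-19. If V.C and VI.B are both followed literally, RT participants are measured later after randomization than SOC participants, by the interval from Visit 1-RT to Visit 2-RT. The documents do not give that interval. Later RT visits could also leave the two arms with different shares of late results.

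What is at stake is the primary comparison. Scoring valid suppressed results as failures shrinks a true difference and costs power. Because the trial is open-label, the choice of rule should not be left until results by arm are visible.

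**Working it through.** **1. The rules side by side, for a suppressed result at a closure visit after the Visit 3 window**

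| Text | Score |
|---|---|
| X.B.1 (study conclusion, Visit 3) | Success, if the closure visit stands in for Visit 3 |
| X.B.4, primary comparison (study conclusion) | Success |
| IV.A, failure rule (result lacking) | Not a failure; a result exists |
| IV.A, outcome (nine months after enrollment) | Not at the stated time |
| X.B.4, failure rule (nine-month endpoint) | Failure, read literally |

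**2. The plan's own power (X.A)**

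Inputs: SOC 68%; RT 76%, 78% or 80%; alpha 0.05 (taken as two-sided; the plan does not say); 420 per arm; 5% invalid tests, so n = 420 × 0.95 = 399.

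Power = Φ[(Δ − 1.96·SE0)/SE1], with SE0 = √(2p̄(1−p̄)/n) and SE1 = √([p1(1−p1) + p2(1−p2)]/n).

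Result: 0.712, 0.891 and 0.973, against 0.69, 0.88 and 0.97 stated. With a continuity correction: 0.684, 0.875 and 0.967. The plan's power is sound.

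**3. Effect of failing late results, equal late share**

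Assumptions, not in the documents: L is the share of each arm measured only at a late closure visit. r is suppression among late attenders relative to their arm's average, set to 1 or 0.5. True rates are 68% v 78%, with n = 420 per arm.

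Scored rate = true rate × (1 − r × L).

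With late results counted: Δ = 0.100, SE0 = 0.03064, SE1 = 0.03044, so power = Φ(1.31) = 0.905.

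| L | r | SOC | RT | Difference (points) | Power |
|---|---|---|---|---|---|
| 5% | 1 | 64.6% | 74.1% | 9.5 | 0.849 |
| 5% | 0.5 | 66.3% | 76.05% | 9.75 | 0.878 |
| 10% | 1 | 61.2% | 70.2% | 9.0 | 0.786 |
| 10% | 0.5 | 64.6% | 74.1% | 9.5 | 0.849 |

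**4. Effect of an imbalance (r = 1, n = 420 per arm)**

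| Late SOC / RT | Scored rates, true 68% v 78% | Difference (points) | Power |
|---|---|---|---|
| 5% / 10% | 64.6% v 70.2% | 5.6 | 0.41 |
| 10% / 5% | 61.2% v 74.1% | 12.9 | 0.98 |

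With no true difference (68% in both arms), either split gives 64.6% v 61.2%. That is 3.4 points toward the arm with fewer late results, and 17.3% of trials reject in that arm's favour (nominal 2.5%). The two directions mirror each other. The 5-point imbalance is itself an assumption.

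**The case against.** The strongest reply is that the plan already lets late results count. IV.A fails only results that are lacking, X.B.1 scores study conclusion, and X.B.4 uses study conclusion shortly before the failure rule. The nine-month endpoint there may be no more than a label for Visit 3. This stands as a reasonable reading. A reader might infer that closure-visit results will be scored as failures; the documents do not establish that. They show only that two rules for the primary endpoint are in force.

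A reader might also infer a bias against RT. That would need VI.B to be followed literally and to leave more RT results late. VI.B and X.B.2 state the opposite intent, and no interval or late share is given. The direction is open.

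The number affected may be small. Under VII enrollment was complete, and sampling at routine attendances continued in both countries. People out of contact with the clinic may also be suppressed less often, which reduces the loss (the r = 0.5 rows).

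Two limits remain. Figure 2 is not shown, so only the visible text can be said to lack window limits. Closure-visit procedures are not listed, so it is an inference, though a natural one, that a viral load is drawn there.

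Missing = failure for people with no result at all is a stated, legitimate choice and is not disputed.

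**Conclusion.** The concern holds as a conflict between rules for the primary endpoint. The text is wrong as written, because following it literally in different places gives different scores for the same result and different follow-up from randomization in the two arms. It is of modest severity: much of the text supports counting late results, and the number of participants affected is unknown.

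For equal late shares of 5% to 10%, the literal failure rule costs about 3 to 12 points of power (0.905 down to 0.88 at best and 0.79 at worst) and 0.25 to 1.0 point of the 10-point difference. These figures rest on assumed late shares, on late attenders being suppressed at the arm average or half of it, and on the plan's 68% v 78%. Unequal late shares could favour either arm. The plan's stated power is not in error.

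**What to change.** Before any analysis by arm, amend X.B.1 and X.B.4:

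1. Define one Visit 3 analysis window, counted from randomization and identical in both arms. Set its limits from pooled visit dates without knowledge of arm or result, wide enough to include COVID-delayed closure visits. Count any study viral load drawn in the window, including those taken at routine attendances; if there are several, use the one nearest nine months. Keep missing = failure for participants with no result in the window.
2. Use the same time origin in Aim 1, IV.A, X.B.1, X.B.2 and X.B.4, and reconcile V.C with VI.B.
3. Repeat the primary analysis without closure-visit results. Report time to Visit 3 and missingness by arm.
4. In any analysis that excludes participants with no result, keep known deaths as failures. If a COVID-affected group is defined, include people whose visit was due before the shutdown but whose tracking was then delayed.

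The cost is a short amendment and some variables derived from dates, with no new data collection. The drawback is that some outcomes will be measured later than nine months, so the endpoint mixes follow-up times; the analysis in item 3 shows whether that matters.
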